7.2.2. Comparisons of Symptoms Between Clinical Sites

To compare symptom background signals, as well as post-infection symptoms, between clinical sites, MJS Symptoms will be summarized by site, for infected participants in [Table 44](#) and uninfected participants in [Table 45](#).

7.2.3. Alternative Definitions of Symptomatic Influenza Infection

While the study was not powered to establish a predictive signature of symptoms for influenza infection, exploratory analysis will be conducted to determine a predictive multi-symptom model to validate in an independent influenza challenge study.

To predict infection status, as defined by two or more days with RT-PCR+ results, the maximum severity of each symptom reported during current infection (for infected participants) or across the entire challenge period (for uninfected participants) will be included as candidate predictors in a penalized logistic regression model (lasso) [4]. The penalization parameter will be selected based on 10-fold cross-validation. The resultant model will be refit without penalization to remove the bias in estimation of the coefficients caused by the penalization parameter, with estimated odds ratios presented in [Table 46](#). The internal performance of the model in the training set will be shown in the receiver operating characteristic (ROC) curve in [Figure 15](#). The optimal cutpoint from the model, as determined by Youden's J statistic [5], will be used in a future validation of these results.

Additionally, the MMID-2 outcome will be compared with the primary symptomatic influenza infection outcome in [Table 47](#). Sensitivity analyses will also be conducted to assess varying thresholds for MJS scores and, separately, for the number of days of detectable viral shedding ([Table 14](#)).

7.2.4. Other Exploratory Clinical Analyses

An exploratory logistic regression model will be fit to assess the associations between baseline characteristics and the development of symptomatic influenza infection post-challenge, in [Table 48](#). Challenge virus dose will be included as a continuous covariate, with sham inoculum being assigned a TCID₅₀ value of zero. Age at baseline (in years), sex (male vs. female), prior receipt of seasonal influenza vaccine or viral challenge (yes vs. no), and clinical site (UMD vs. DU) will be included as other covariates.

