15. Modified Jackson Score to be obtained on the evening of Day -2 and in the morning and afternoon of each day of confinement (Approximately at 8:00 AM and after 3:00 PM) and on Day 15 during visit. Assure AM assessment on Study Day 1 is performed prechallenge.

16. Unsolicited AEs will be monitored for approximately 28 days post challenge. Review of FLU-PRO for indicators of possible severe influenza associated illness (signs, symptoms, or lab findings).

17. ECG to be performed at screening, on Study Day 6, and as clinically indicated. Sites will consult a cardiologist if ECG is abnormal to determine clinically necessary work up.

18. Among female subjects of childbearing potential, a repeat urine pregnancy test will be performed locally before CXR performed if > 7 days have passed since the negative serum pregnancy test was drawn.

19. Negative drug urine toxicology result (amphetamines, cocaine, and opiates) required on screening and (amphetamines, cocaine, opiates) on admission to the challenge unit, unless the drug is deemed acceptable by the Investigator.

20. Screening Safety/Eligibility Labs: white blood cells (WBCs), absolute lymphocyte count, hemoglobin, platelets, alanine transaminase (ALT), and creatinine (Cr).

21. Follow-Up Safety Labs: Study Days 2, 4, and 8, and as clinically indicated: white blood cells (WBCs), absolute lymphocyte count, hemoglobin, platelets, and alanine transaminase (ALT), and creatinine (Cr).

22. Including HAI, MN and NAI antibody titers on Visits 00C (Day -1) 8, 9, 10 and 11.

23. Multiplex respiratory virus assay to include SARS-CoV-2 to be performed at each site at the time points listed above. Positive results prior to influenza virus challenge will result in subject exclusion from the study. No respiratory virus testing will be done on the day of challenge. Quantitative PCR will not be done at screening.

24. If indicated.

25. If terminates study < Study Day 8 and procedure not performed on day study terminated.

Protocol 20-0005	Version 8.0
H3N2 Dose-Ranging Challenge	04May2023

26. If terminates study early and procedure not scheduled to be performed on day study terminated or if missed study procedure on scheduled day.

[figure not shown]
27. To achieve baseline data for physiological biomarkers (e.g., heartrate variability, sleep patterns, etc.).

- 28. If the Garmin and/or Oura ring is not able to be distributed at screening this will not be a protocol deviation.

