#### 9.5.7 Sub-Group Analyses

No explicit sub-group analyses beyond those relating to the dose of study challenge received are planned. However, exploratory analysis may be conducted to examine potential impacts of baseline characteristics such as sex or baseline HAI, NAI, or MN titers.

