12. REPORTING CONVENTIONS

P-values ≥ 0.001 and ≤ 0.999 will be reported to 3 decimal places; p-values less than 0.001 will be reported as “ <0.001 ”. The mean, standard deviation, and other statistics will be reported to 1 decimal place greater than the original data. The minimum and maximum will use the same number of decimal places as the original data. Proportions will be presented as 2 decimal places; values greater than zero but <0.01 will be presented as “ <0.01 ”. Percentages will be reported to the nearest whole number; values greater than zero but $<1\%$ will be presented as “ <1 ”; values greater than 99% but less than 100% will be reported as $>99\%$. Estimated parameters, not on the same scale as raw observations (e.g., regression coefficients) will be reported to 3 significant figures.

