[Repeat for any additional symptom(s) selected in lasso procedure]

Notes: XX participants in the Safety population included in the model; the infection outcome is defined as two or more study days with RT-PCR+ tests at any point during the challenge period. The maximum severity of each MJS symptom during the infection period, or across the challenge period for the uninfected participants, is utilized in the set of candidate predictors.

The optimal value for the penalization parameter determined using 10-fold cross-validation.

Unbiased coefficient estimates obtained by refitting selected covariates in logistic regression model.

Hosmer and Lemeshow Goodness of Fit p-value = 0.xxx.

Table 47: Comparison of Symptomatic Influenza Infection to Mild-to-Moderate Influenza Disease, Safety Population

Variable	10 ⁴ TCID ₅₀ Challenge Virus (N=X)		10 ⁵ TCID ₅₀ Challenge Virus (N=X)		10 ⁶ TCID ₅₀ Challenge Virus (N=X)		Sham Inoculum (N=X)		All Participants (N=X)	
	MMID-2 n (%)	No MMID-2 n (%)	MMID-2 n (%)	No MMID-2 n (%)	MMID-2 n (%)	No MMID-2 n (%)	MMID-2 n (%)	No MMID-2 n (%)	MMID-2 n (%)	No MMID-2 n (%)
Symptomatic Influenza Infection	x (x.x)	x (x.x)	x (x.x)	x (x.x)	x (x.x)	x (x.x)	x (x.x)	x (x.x)	x (x.x)	x (x.x)
No Symptomatic Influenza Infection	x (x.x)	x (x.x)	x (x.x)	x (x.x)	x (x.x)	x (x.x)	x (x.x)	x (x.x)	x (x.x)	x (x.x)

Notes: N = Number of participants in the Safety population; n = Number of participants reporting the given combination of Symptomatic Influenza Infection and MMID-2 outcomes after challenge.

Table 48: Logistic Regression Model to Assess the Associations Between Baseline Characteristics and Development of Symptomatic Influenza Infection, Safety Population

Model Parameter	Parameter Estimate	SE	p-value	Odds Ratio	95% CI
Intercept	x.xx	x.xx	x.***	-	-
Challenge Virus Dose (TCID ₅₀)	x.xx	x.xx	x.***	x.xx	(x.xx, x.xx)
Age at Baseline (Years)	x.xx	x.xx	x.***	x.xx	(x.xx, x.xx)
Sex (Male vs. Female)	x.xx	x.xx	x.***	x.xx	(x.xx, x.xx)
Prior Receipt of Seasonal Influenza Vaccine or Viral Challenge (Yes vs. No)	x.xx	x.xx	x.***	x.xx	(x.xx, x.xx)
Clinical Site (UMD vs. DU)	x.xx	x.xx	x.***	x.xx	(x.xx, x.xx)

Notes: XX participants in the Safety population included in the model; the symptomatic influenza infection outcome is defined as two or more study days with RT-PCR+ tests and, separately, a cumulative Modified Jackson Score of at least 6 over any 5-day window during the challenge period. Hosmer and Lemeshow Goodness of Fit p-value = 0.xxx.

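### The exploratory logistic model enters dose as raw TCID50 with sham at zero, so its dose odds ratio prints as 1.00 (1.00, 1.00), and with 10^6 enrolled it forces sham, 10^4 and 10^5 to nearly equal fitted risk

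*SAP*

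**What the plan says.** SAP 7.2.4 gives the model's purpose: "An exploratory logistic regression model will be fit to assess the associations between baseline characteristics and the development of symptomatic influenza infection". Dose is an adjustment term: "Challenge virus dose will be included as a continuous covariate, with sham inoculum being assigned a" TCID50 value of zero. The other covariates are age, sex, prior seasonal vaccine or viral challenge, and site. Neither the section nor the table mentions a logarithm, a rescaling or dose categories. Since log10 of zero is undefined, assigning zero to sham points to the raw scale.

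The output is SAP Table 48, titled "Logistic Regression Model to Assess the Associations Between Baseline Characteristics and Development of Symptomatic Influenza Infection, Safety Population". Its dose row has TCID50 as the unit, and its shell gives the odds ratio and confidence limits to two decimals. SAP 12 adds: "Estimated parameters, not on the same scale as raw observations (e.g., regression coefficients) will be reported to 3 significant figures".

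On baseline antibody, Protocol 9.5.7 says that "exploratory analysis may be conducted to examine potential impacts of baseline characteristics such as sex or baseline HAI, NAI, or MN titers". Footnote 22 of the Protocol's Schedule of Activities shows that titers are available before challenge: "Including HAI, MN and NAI antibody titers on Visits 00C (Day -1) 8, 9, 10 and 11". They are not in the model.

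**The concern.** The doses are spaced 10-fold, and Protocol 9.3.2 assumes that the attack rate rises with dose. A linear term in raw TCID50 does not suit that spacing, for two reasons.

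- **Display.** An odds ratio per single TCID50, on a scale that runs to a million, is too close to 1 to be seen at the planned precision. The study report could show a significant p-value for dose beside an odds ratio of 1.00 (1.00, 1.00).
- **Fit.** On the raw scale sham, 10^4 and 10^5 sit together at one end and 10^6 stands alone at the other. The model then adjusts for little more than 10^6 against everything else. Its stated purpose is the effect of baseline characteristics. Any characteristic spread unevenly over the lower doses would absorb part of the dose difference that the model cannot represent. Protocol 6.3.2 allows cohorts to be split between the two sites, so site could be such a characteristic.

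**Working it through.** **Inputs from the documents.** Cohorts have 12 active plus 1 sham at 10^4 and 10^5 (up to three each) and 17 active plus 1 sham at 10^6 (two cohorts). The maximum is 6 × 13 + 2 × 18 = 114, of which 6 × 12 + 2 × 17 = 106 are active, as stated. The shortest path through all three doses is 13 + 13 + 18 + 18 = 62, also as stated, and gives 4 sham, 12, 12 and 34. The documents give no figure for the Table 48 model itself.

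**Assumptions.** The documents target a 55-80% attack rate at the optimal dose and give no rates for the other doses. All attack rates below are therefore assumed.

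**Step 1: the printed odds ratio.** The model is logit(p) = a + b × dose, fitted to expected counts. With 4/12/12/34 participants and 0.1/20/40/65%, b = 1.815 × 10^-6 per TCID50 with standard error 5.94 × 10^-7. Then exp(1.815 × 10^-6 ± 1.96 × 5.94 × 10^-7) gives 1.0000018 (1.0000007 to 1.0000030). Both the shell format and 3 significant figures print 1.00 (1.00, 1.00). To print 1.01 the odds ratio must reach 1.005, so b must reach ln(1.005) = 0.00499. Over 10^6 TCID50 that is a log-odds change of about 5,000. In 3,000 simulated trials of the full model on this path, no estimate or limit printed as anything but 1.00.

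**Step 2: fitted risks.** The same b gives odds ratios against sham of exp(0.018) = 1.02 at 10^4, exp(0.181) = 1.20 at 10^5 and exp(1.815) = 6.1 at 10^6. The lower groups are tied together by the coding. Over several assumed curves:

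| Participants: sham/10^4/10^5/10^6 | Assumed rates (%) | Fitted rates (%) | OR per TCID50 |
|---|---|---|---|
| 4/12/12/34 | 0.1/20/40/65 | 24/24/27/65 | 1.0000018 |
| 8/36/36/34 | 0.1/20/40/65 | 25/25/28/66 | 1.0000018 |
| 6/12/36/34 | 0.1/20/60/70 | 41/42/44/72 | 1.0000013 |
| 4/12/12/34 | 0.1/2/10/90 | 4/4/6/90 | 1.0000054 |
| 4/12/36/none | 0.1/30/75 | 19/23/75 | 1.000026 |

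In the first row sham is about 24 points too high, 10^5 is 13 too low and 10^4 is 4 too high. In the fourth row every group is within about 4 points.

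**Step 3: the alternative.** With log10(TCID50) in virus recipients and the first row's rates, the odds ratio is 2.74 per 10-fold dose (1.30 to 5.76), with fitted rates 20/40/65%. With 114 participants it is 2.73 (1.59 to 4.67).

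**Step 4: other covariates.** Take the first row with no true site effect, and split sham and 10^6 evenly between sites. If one site supplies 25% of the 10^4 and 75% of the 10^5 recipients, the fitted site odds ratio with raw dose is 1.17 (0.39 to 3.48). If each lower dose comes wholly from one site, it is 1.37 (0.46 to 4.08). Log10 dose in virus recipients gives 0.99 both times. With an even split both codings give 1.00.

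**The case against.** The strongest reply is that the model is exploratory, concerns baseline characteristics and carries dose only for adjustment. Dose selection rests on attack rates by dose group with exact intervals (Protocol 9.5.2, SAP 7.1.1, Table 14). All of that stands.

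The dose row is also not empty. Table 48 prints a p-value, and in the simulations the raw-dose term had p < 0.05 in 86-91% of trials, against 73-82% for log10 dose in virus recipients; the two fits use different participants. A coefficient given to 3 significant figures, as SAP 12 asks, would be legible even though the two-decimal shell would show 0.00. A Hosmer-Lemeshow p-value is planned and might flag poor fit. None of this gives the reader a usable effect size.

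Harm to the other covariates is conditional. In a simulation of the five-covariate model with a balanced covariate (sex, true log odds ratio 0.69), the median estimate was 0.78 with raw dose and 0.82 with log10 dose. Bias appears only with imbalance across doses, which the documents neither show nor rule out.

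A reader might infer that every lower dose is misfitted. The fourth row of the table shows otherwise. A reader might also infer that leaving out baseline HAI is an error. Protocol 9.5.7 makes that analysis optional, SAP Tables 49-56 already summarise baseline titers by dose, infection and symptomatic status, and no titer imbalance between doses is shown. Eligibility at 1:40 or below leaves about four titer levels. If each two-fold step had an odds ratio of 0.5 or 0.7 (assumed), a 62-person trial would detect it in 73% or 29% of cases.

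**Conclusion.** The dose coding should be corrected. Two results need little or no assumption about attack rates. First, the dose odds ratio prints as 1.00 (1.00, 1.00) for any realistic effect. The exception is a fit that separates, for instance if only 10^4 were given and no sham participant were a case; the dose term is then not estimable at all. Second, whenever 10^6 is enrolled, sham, 10^4 and 10^5 receive nearly equal fitted risk.

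The size of the misfit does rest on assumed rates. The examples range from within about 4 points in every group to about 41 points for sham and 22 for 10^4. The possible bias in a site odds ratio, 1.17 to 1.37 against a true 1, also rests on assumed site splits and is small beside its confidence interval.

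A reader might take this as a fault in the trial's dose-response evidence or in the choice of optimal dose. The documents do not support that: Table 48 feeds neither escalation nor dose selection, and Table 14 is estimated separately by dose group. The fault is confined to one exploratory model, but it is certain enough and cheap enough to mend before the analysis is run.

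**What to change.** In SAP 7.2.4, fit the model in virus recipients of the Safety population with log10(TCID50), so that the odds ratio is per 10-fold dose. Dose as a factor among virus recipients is an acceptable alternative. Keep age, sex, prior vaccine or challenge, and site. Omit the dose term if only one dose was given, since it is then constant. Relabel the dose row of Table 48, and change its title and footnote to name the virus recipients.

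Rescaling alone, for example per 10^6 TCID50, would cure the display but not the forced equality of the lower groups. Keeping sham as a category would cause separation if no sham participant is a case.

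The cost is a short SAP edit, a changed analysis set for this one model, and the loss of its sham participants (4 on the 62-person path, 8 on the 114-person path), who say nothing about the slope between virus doses. No new data are needed.

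Optionally, add log2 Day -1 HAI titer in a sensitivity model, stating the analysis population, because SAP 7 assigns analyses of immune responses to the ITT population. With five covariates already in a small data set, it is better kept out of the main model.

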8. IMMUNOLOGICAL EVALUATION

8.1. Secondary Immunogenicity Analyses

Only secondary immunogenicity analysis of HAI, MN, NAI, and anti-HA stalk assay data will be included in the interim CSR. Exploratory immunogenicity analysis not included in this SAP will be planned in a separate SAP addendum to this analysis plan and presented in an addendum to the CSR or one or more separate reports for the purposes of manuscript development.

Immunogenicity analyses are planned in the ITT population. If 10% or more of the timepoints utilized in the immunogenicity analyses would be excluded by the list given in [Section 5.3.3](#) to define the Per Protocol population, the secondary immunogenicity analyses will be conducted in the PP population as a sensitivity analysis.

HAI, MN, and anti-HA stalk antibody titers against the challenge strain will be analyzed by time point, challenge dose group, and infection status in [Table 49](#), [Table 50](#), and [Table 52](#), respectively. Geometric mean titers (GMTs) will be computed at each time point for each group, as well as geometric mean fold-rise (GMFR) and seroconversion (as defined in [Section 3.2.7](#)) at each post-challenge time point. Associated 95% CIs will be presented as well. GMTs and 95% CIs will be presented graphically in [Figure 16](#) and [Figure 18](#), and the entire distribution of titers reported at each visit will be presented in reverse cumulative distribution (RCD) curves in [Figure 19](#), [Figure 20](#), and [Figure 22](#).

The assays will be analyzed similarly by symptomatic infection status in [Table 53](#), [Table 54](#), and [Table 56](#).

Antibody titers will be listed, by assay, in [Listing 11](#).

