1. To assess the safety profile of a live recombinant influenza strain (A/Texas/71/2017 (H3N2), clade 3C3a) following challenge in healthy adult volunteers	
 
a. Number of adverse events (AE) reported from challenge through Day 29
 
b. Percentage of subjects reporting any AE from challenge through Day 29
 
c. Number of serious adverse events (SAE) from challenge through Day 57
 
d. Percentage of subjects reporting an SAE at any time from challenge through Day 57
 

2 T. 1	Demonstration of and instances (1 1 1 1
2. To describe the host serum hemagglutination inhibition and microneutralization antibody responses at baseline and post-challenge	
 
a. Percentage of subjects with serological conversion defined as a minimum 4-fold rise in post-challenge serum antibodies (HAI and MN) to influenza infection at Days 8, 15, and 29, or latest time point available, post challenge compared to baseline (Day - 1).
 
b. HAI and MN antibody geometric mean titers (GMTs) at baseline (Day -1) and GMTs and Geometric Mean Fold Rise (GMFR) post-challenge at Days 8, 15, and 29, or latest time point available
 

3. To describe anti-HA-stalk antibody titer at baseline and post-challenge	
 
a. Percentage of subjects with serological conversion defined as a minimum 4-fold rise in post-challenge HA-stalk specific serum antibody response to HA group 2 stem domains at any day up to Day 29, or latest time point available, post challenge compared to baseline (Day -1).
 
b. For HA-stalk specific response, the GMTs to HA group 2 stem domains at baseline (Day -1), and GMTs and GMFR at approximately Days 8, 15, and 29, or latest time point available.
 

Exploratory	
1. To describe the host serum neuraminidase inhibiting antibody responses at baseline and post-challenge	
 
a. Percentage of subjects with serological conversion defined as a minimum 4-fold rise in post-challenge serum antibodies (NAI) to influenza infection at Days 8, 15, and 29, or latest time point available, post challenge compared to baseline (Day -1).
 
b. NAI antibody geometric mean titers (GMTs) at baseline (Day -1) and GMTs and Geometric Mean Fold Rise (GMFR) post-challenge at Days 8, 15, and 29, or latest time point available
 

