#### 9.5.3.2 Analysis of Secondary Immunological Endpoints

Secondary immunological objectives include describing the host serum antibody (HAI and MN) responses and anti-HA-stalk antibody responses at baseline and post-challenge.

For these titer data, GMTs and the proportions of subjects achieving seroconversion, defined as a minimum 4-fold rise in titer post-challenge, will be presented by challenge dose group and visit. Geometric mean fold-rise (GMFR) for anti-HA-stalk antibody titers will be included for post-challenge visits as well. Confidence intervals corresponding to these statistics will be computed for each group and visit as well. Hypothesis testing may be performed for select immunological endpoints and time points, which will be pre-specified in the SAP.

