	1: Just Noticeable	xx (xx.x)	xx (xx.x)	xx (xx.x)	xx (xx.x)	xx (xx.x)
	2: Bothersome from Time to Time	xx (xx.x)	xx (xx.x)	xx (xx.x)	xx (xx.x)	xx (xx.x)
	3: Bothersome Most or All of the Time	xx (xx.x)	xx (xx.x)	xx (xx.x)	xx (xx.x)	xx (xx.x)
		Felt Hot				
		Extent: 0 (Not at all)	1 (A little bit)	2 (Somewhat)	3 (Quite a bit)	4 (Very much)
Feverish	Any Severity	xx (xx.x)	xx (xx.x)	xx (xx.x)	xx (xx.x)	xx (xx.x)
	0: None	xx (xx.x)	xx (xx.x)	xx (xx.x)	xx (xx.x)	xx (xx.x)
	1: Just Noticeable	xx (xx.x)	xx (xx.x)	xx (xx.x)	xx (xx.x)	xx (xx.x)
	2: Bothersome from Time to Time	xx (xx.x)	xx (xx.x)	xx (xx.x)	xx (xx.x)	xx (xx.x)
	3: Bothersome Most or All of the Time	xx (xx.x)	xx (xx.x)	xx (xx.x)	xx (xx.x)	xx (xx.x)
		Trouble Breathing				
		Extent: 0 (Not at all)	1 (A little bit)	2 (Somewhat)	3 (Quite a bit)	4 (Very much)
Shortness of Breath	Any Severity	xx (xx.x)	xx (xx.x)	xx (xx.x)	xx (xx.x)	xx (xx.x)
	0: None	xx (xx.x)	xx (xx.x)	xx (xx.x)	xx (xx.x)	xx (xx.x)
	1: Just Noticeable	xx (xx.x)	xx (xx.x)	xx (xx.x)	xx (xx.x)	xx (xx.x)
	2: Bothersome from Time to Time	xx (xx.x)	xx (xx.x)	xx (xx.x)	xx (xx.x)	xx (xx.x)
	3: Bothersome Most or All of the Time	xx (xx.x)	xx (xx.x)	xx (xx.x)	xx (xx.x)	xx (xx.x)

Notes: N = Number of infected participants in the Safety population; n = Number of participants reporting each symptom. Earache from Modified Jackson Score tool not included, with no corresponding FLU-PRO data for comparison.

Similar Table:

Table 42: Cross-Tabulation of the Maximum Severity of Solicited Influenza Symptoms and Participant-Reported FLU-PRO Symptoms During the Challenge Period, Uninfected Participants in the Safety Population

[Implementation Note: Update the footnote from the shell above for uninfected participants.]

Table 43: Summary of Symptom Scores by Challenge Dose Group and Infection Status, Safety Population

Symptom Score	Statistic	10 ⁴ TCID ₅₀ Challenge Virus (N=X)			10 ⁵ TCID ₅₀ Challenge Virus (N=X)			10 ⁶ TCID ₅₀ Challenge Virus (N=X)			Sham Inoculum (N=X)		
		Infected ^a	Uninfected	All Participants in Dose Group	Infected ^a	Uninfected	All Participants in Dose Group	Infected ^a	Uninfected	All Participants in Dose Group	Infected ^a	Uninfected	All Participants in Dose Group
Maximum Cumulative Modified Jackson Score (Total)	Mean (95% CI) ^b	x.x (x.x, x.x)	x.x (x.x, x.x)	x.x (x.x, x.x)	x.x (x.x, x.x)	x.x (x.x, x.x)	x.x (x.x, x.x)	x.x (x.x, x.x)	x.x (x.x, x.x)	x.x (x.x, x.x)	x.x (x.x, x.x)	x.x (x.x, x.x)	x.x (x.x, x.x)

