14.2.1 Immunogenicity Response Figures

Figure 16: Geometric Mean Titers and 95% CI for Hemagglutination Inhibition and Microneutralization Antibodies Against A/Texas/71/2017 (H3N2), clade 3C3a Virus, by Study Visit and Challenge Dose Group – ITT Population

[Implementation note: There will be a separate panel for each combination of assay and infection status, with the 4 challenge dose groups in different colors with different line types within each panel. The paneling columns will be Infected and Uninfected, and the paneling rows will be HAI and MN.]

[figure not shown]
Similar Figures:

Figure 17: Geometric Mean Titers and 95% CI for Neuraminidase Inhibition Antibodies Against A/Texas/71/2017 (H3N2), clade 3C3a Virus, by Study Visit and Challenge Dose Group – ITT Population

Figure 18: Geometric Mean Titers and 95% CI for Anti-HA Stalk Antibodies Against A/Texas/71/2017 (H3N2), clade 3C3a Virus, by Study Visit and Challenge Dose Group – ITT Population

Figure 19: Reverse Cumulative Distribution of Hemagglutination Inhibition Antibody Titers Against A/Texas/71/2017 (H3N2), clade 3C3a Virus, by Study Visit and Challenge Dose Group

[Implementation note: There will be a separate panel for each combination of study day and infection status, with the 4 challenge dose groups in different colors with different line types within each panel. The paneling columns will be Infected and Uninfected, and the paneling rows will be study days.]

Similar Figures:

Figure 20: Reverse Cumulative Distribution of Microneutralization Antibody Titers Against A/Texas/71/2017 (H3N2), clade 3C3a Virus, by Study Visit and Challenge Dose Group

Figure 21: Reverse Cumulative Distribution of Neuraminidase Inhibition Antibody Titers Against A/Texas/71/2017 (H3N2), clade 3C3a Virus, by Study Visit and Challenge Dose Group

Figure 22: Reverse Cumulative Distribution of Hemagglutination Inhibition Antibody Titers Against A/Texas/71/2017 (H3N2), clade 3C3a Virus, by Study Visit and Challenge Dose Group

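### No planned antibody table or figure reports a whole dose group, although protocol 9.5.3.2 plans the secondary antibody estimates by dose group and visit

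*SAP*

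**What the plan says.** **Protocol.** Section 9.5.3.2 covers HAI, MN and anti-HA stalk. It opens with "For these titer data, GMTs and the proportions of subjects achieving seroconversion" and says that these "will be presented by challenge dose group and visit", with confidence intervals for each group and visit. For fold-rise it says only: "Geometric mean fold-rise (GMFR) for anti-HA-stalk antibody titers will be included for post-challenge visits as well". GMFR for HAI and MN comes from the secondary endpoints in section 3, which list "HAI and MN antibody geometric mean titers (GMTs) at baseline (Day -1) and GMTs and Geometric Mean Fold Rise (GMFR) post-challenge". Neither section conditions on infection. Section 9.5.1 makes challenge dose group the default for summaries, with sham pooled. It names shedding status as one of several further groupings for some analyses.

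**SAP.** Section 8.1 says: "HAI, MN, and anti-HA stalk antibody titers against the challenge strain will be analyzed by time point, challenge dose group, and infection status". The shells follow that sentence:

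- Tables 49-52: every dose column, sham included, is divided into Infected and Uninfected, with no combined column.
- Tables 53-56: four symptom-by-infection columns, and dose is dropped.
- Figures 16-18 (GMTs): "There will be a separate panel for each combination of assay and infection status, with the 4 challenge dose groups in different colors".
- Figures 19-22 (reverse cumulative distributions): panels by study day and infection status.

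NAI, which is exploratory, follows the same pattern under SAP 8.2. SAP section 14 reports no substantive departure from the protocol's planned analyses. Table 43, for symptom scores, does carry a column headed "All Participants in Dose Group".

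**The concern.** The protocol's unit of estimation is the dose group at a visit. The SAP's unit is the infected or uninfected part of a dose group at a visit. The dose-group estimate has dropped out of every summary display without being declared.

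Infection status (SAP 3.2.3) is defined by RT-PCR results on at least two days after challenge. Protocol 9.3.2 assumes that the attack rate rises with dose, so the infected share should be expected to differ between dose groups. A split column describes participants selected on an outcome of the challenge. The protocol asks for the response of everyone given a dose, and that response mixes the two strata in proportions that vary with dose.

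Tables 49, 50 and 52 are marked for the topline report. SAP 5.2 treats topline results as final and plans to present part of them at a 2023 network meeting. The gap would therefore carry into the first reported secondary results.

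**Working it through.** **1. The documents' own interval.** Both documents illustrate dose-group precision with 15 events in 30 participants and an exact 95% CI of 31.3% to 68.7%. The Clopper-Pearson formula gives the same limits. That example concerns the attack rate. The documents give no antibody figure, so there is none to dispute.

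**2. Inventory of antibody displays.**

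| Display | Dose group kept? | Split by infection status? | Whole dose group shown? |
|---|---|---|---|
| Tables 49-52 | yes | yes | no |
| Tables 53-56 | no | yes, crossed with symptoms | no |
| Figures 16-18 | yes | yes | no |
| Figures 19-22 | yes | yes | no |

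That is 8 tables and 7 figures, with no whole-group estimate among the 15. Listing 11 gives individual titers only. SAP 8.1 does say that statistics are computed for each group, which could be read as dose group. The shells rule that reading out, and SAP 5.1 summarises titers within clinical outcome groups.

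**3. What the split leaves out (assumed inputs).** Suppose that at every dose seroconversion is 80% in infected and 10% in uninfected participants, and GMFR is 8 and 1.2. Let s be the infected share. Then:

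- dose-group seroconversion = 0.80s + 0.10(1 − s)
- dose-group GMFR = 8^s × 1.2^(1 − s)

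| s | Seroconversion | GMFR |
|---|---|---|
| 0.30 | 0.24 + 0.07 = 31% | 2.1 |
| 0.55 | 0.44 + 0.045 = 48.5% | 3.4 |
| 0.80 | 0.64 + 0.02 = 66% | 5.5 |

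The stratum percentages and fold-rises would be the same in all three rows. Equal stratum results across doses is a simplifying assumption chosen to isolate the effect of the infected share.

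**4. Precision (assumed counts, n = 30).** The planned columns would show 16/20 = 80% (56.3% to 94.3%) and 1/10 = 10% (0.3% to 44.5%). The estimate that the protocol asks for is 17/30 = 56.7% (37.4% to 74.5%), and no shell has a place for it.

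**5. Can it be rebuilt?** Largely, yes. For seroconversion, n and the percentage give the counts, and the counts give the exact interval, as 16 + 1 = 17 of 30 shows. For GMT and GMFR, each stratum's n, estimate and t-based CI give its log-scale mean m_k and SD s_k. The whole-group mean m is Σn_k·m_k / N, and the total sum of squares is Σ(n_k − 1)s_k² + Σn_k(m_k − m)². This is approximate because of rounding. It also needs the t-interval, not the bootstrap alternative that SAP 5.1 allows, and the printed n must apply to GMFR. Listing 11 allows a direct calculation.

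**The case against.** The other side has a good deal in its favour.

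- **The split is foreseen.** Protocol 9.5.1 allows grouping by shedding status, protocol 9.4 allows analyses in infected subjects, and SAP 5.1 openly refers to clinical outcome groups. Tables 49-52 keep dose and visit and add a stratum. This stands as a reason to keep the split. It does not justify removing the whole-group estimate that 9.5.3.2 specifies.
- **Nothing is lost for good.** A reader might infer that the dose-group GMT or GMFR and its interval cannot be recovered. The documents do not support that, as step 5 shows.
- **Doses would not look alike.** A reader might infer that doses with very different immune take would be indistinguishable. Every column has an n row, so with 30 per dose, infected shares of 30% and 80% would print as 9/21 and 24/6. Table 14 also gives the infected percentage and its CI by dose. The reader would still have to do the weighting unaided.
- **Seroconversion is not the only swab-independent measure of take.** The protocol also lists nasal IgA, plasmablasts, influenza-specific B and T cells, and possible lavage RT-PCR or culture. These are exploratory, and some are optional or limited to subsets.
- **GMFR is only partly in 9.5.3.2.** That section names it for anti-HA stalk alone. For HAI and MN it rests on the endpoints in section 3, which do not set a dose grouping for it.
- **No dose comparison is tested.** SAP 8.1 plans no between-dose antibody test, the objectives are to describe, and no power or precision was targeted. So the SAP commits no invalid test. The risk lies in how readers compare the columns.

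**Conclusion.** The point holds as a gap between protocol and SAP. The whole-dose-group GMT and seroconversion for three assays, GMFR for anti-HA stalk, and their confidence intervals are specified in protocol 9.5.3.2. GMFR for HAI and MN is a secondary endpoint in section 3. None of these appears for a whole dose group in any of the 15 antibody displays, and SAP section 14 does not say so. The inventory rests only on the SAP text and shells. The 31%, 48.5% and 66% figures rest on assumed stratum results and show the mechanism, not an expected finding.

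The consequence is moderate. A reader might infer that the choice of dose is at risk. It is not: protocol 9.5.2 selects the optimal dose on attack rate and halting criteria, and antibody results do not enter escalation. What is missing is a descriptive secondary estimate that can be rebuilt from planned output but that the protocol says will be presented. It should be fixed, preferably before the topline report, because three of the affected tables are in it.

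**What to change.** - Add a column headed "All Participants in Dose Group", as in Table 43, to each dose group and to sham in Tables 49, 50 and 52. It should show n, GMT, GMFR, seroconversion and 95% CIs by visit. Do the same in exploratory Table 51.
- Add an all-participants panel to Figures 16-22.
- State in SAP 8.1 that the whole-group column is the analysis planned in protocol 9.5.3.2, and that the infected/uninfected columns are descriptive. Tables 53-56 can stay as they are.
- If the sponsor prefers the split alone, declare and justify the change in SAP section 14.

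The cost is a shell edit and minor programming. No new data are needed.
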